## **1. Background**

Over the past 20 years, there has been a dramatic increase in the rates of obesity in the United States. The US National Institutes of Health defines obesity as a body mass index (BMI) of  $\geq 30$ - $39.9 \text{ kg/m}^2$  and morbid obesity as a BMI of  $\geq 40 \text{ kg/m}^2$ , using height and weight to obtain BMI. According to data published by the US Department of Health and Human Services, over 35 percent of Americans were considered obese in 2009-2010. Obese patients are at increased risk for cardiovascular and venous thromboembolic events due to associated comorbidities including hyperlipidemia, glucose intolerance, hypertension, and a sedentary lifestyle. Treatment of cardiovascular and venous thromboembolic events often includes anticoagulation with low molecular weight heparin. Thus, there are a significant number of obese patients that will need therapeutic anticoagulation.

Landmark clinical trials that led to the approval of the low molecular weight heparin, enoxaparin, for treatment of venous thromboembolism and acute coronary syndromes did not list obesity as an exclusion criterion, but little data is available on the outcomes in this population due to underrepresentation in those trials. Data on the safety and efficacy of enoxaparin in the obese population is derived mainly from observational or pharmacokinetic studies. The implications of limited data can be very serious since appropriate dosing is crucial to ensure efficacy and to prevent adverse events including bleeding complications.

After low molecular weight heparin is administered, it predominantly concentrates in the plasma and highly vascular tissues with little distribution into fat tissue. Since dosing is based on weight, obese patients may receive higher doses; however, because there is low distribution into fat tissue this may result in elevated anti-Xa levels and thus they can be easily overdosed. It has been shown that anti-Xa activity is increased appropriately when the drug is administered to patients based on total body weight up to 144 kg. The American College of Chest Physicians Evidence-based clinical practice guidelines recommend monitoring of anti-Xa levels in obese patients. Enoxaparin has both anti-Xa and anti-IIa activity however, because of the higher anti-Xa:IIa ratio, anti-Xa levels are used as a marker of activity. It has been suggested that the incidence of bleeding is increased when anti-Xa levels are elevated; however, data are conflicting.

There is limited data available to guide dosing of patients above 150 kg. The largest prefilled syringe is 150 mg and has resulted in many clinicians capping the dose at 150 mg. A pharmacokinetic study in 48 healthy obese volunteers (BMI 30-40  $\text{kg/m}^2$ ) at a single study center showed that dosing based on total body weight achieved similar maximum anti-Xa levels in both obese and non-obese patients, 1.563 IU/ml and 1.488 IU/ml respectively. The authors recommended no need to modify dosing in obese patients; however, this trial used 1.5 mg/kg daily, included healthy volunteers, and the highest weight studied was only 144 kg. A prospective study in hospitalized patients with a BMI $>30 \text{ kg/m}^2$  evaluated anti-Xa levels using 1 mg/kg twice daily. Forty five percent of patients achieved a therapeutic anti-Xa level with the mean being 1.17 IU/ml. There was no difference in anti-Xa levels between those with and without bleeding episodes. The authors concluded no dose adjustment necessary in this study. The results from the above studies suggest standard dosing produces similar anti-Xa levels in non-obese and obese patients above 30  $\text{kg/m}^2$ .

A retrospective study evaluating the dosing of enoxaparin in 26 morbidly obese hospitalized patients (BMI  $\geq 40 \text{ kg/m}^2$ ) also evaluated anti-Xa levels. A median dose of 0.8 mg/kg based on total body weight was utilized with maximum doses up to 150 mg. Forty six percent of patients achieved a goal anti-Xa level and 38% of patients were above the anti-Xa goal. The weight cut-off of 150 kg did not result in statistically significant differences in mean anti-Xa levels (1.12 IU/ml in patients over 150 kg vs 0.81 IU/ml in patients over 150 kg,  $p>0.05$ ). Even though 4 out

of 10 patients with a supratherapeutic anti-Xa level experienced more bleeding events, these patients were noted to have additional risk factors for bleeding. This trial suggests that lower initial dosing of enoxaparin could be utilized in the morbidly obese population since the majority of anti-Xa levels were at or above goal.

There are a few studies looking at clinical outcomes that may be influenced by the dosing dilemma of enoxaparin in obesity. A subgroup analysis of the SYNERGY trial evaluated if BMI affected outcomes in hospitalized NSTEMI patients. Patients at both extremes of weight were dosed with enoxaparin 1mg/kg based on total body weight with no capping of doses. Major bleeding, using the TIMI definition, during hospitalization was lower for patients with a BMI above 35 compared to those with a BMI below 20 (8.8% vs. 11.4%). In addition, obesity did not have an effect on the efficacy outcomes of mortality or myocardial infarction at 30 days and 6 months which led authors to conclude those with normal renal function should be dosed with 1 mg/kg of actual body weight regardless of body weight. However, only 3.5% of patients had a BMI>40 kg/m^2, thus, more research in that group was recommended. A meta-analysis that included hospitalized NSTEMI patients with a BMI>30 kg/m^2 also showed no increase in major bleeding in obese patients who were dosed based on total body weight. In contrast, an observational study using the CRUSADE database of hospitalized NSTEMI patients showed an increased incidence of non CABG related bleeding in patients weighing >150kg receiving standard 0.95-1.05 mg/kg dosing compared to those receiving a lower initial dose of <0.95 mg/kg (11.4% vs. 6.5%, OR 2.42). However, as seen in the previous studies, patients over 150 kg represented a small portion of the study population (0.92%) therefore more safety data is warranted in that group.

The Chest guidelines have recommended a dosing nomogram to adjust low molecular weight heparin doses; however, the study used to validate the nomogram was performed in a pediatric patient population. Even though guidelines suggest monitoring and adjusting doses based on anti-Xa levels, little guidance is given on whether the initial dose should be empirically decreased to a more conservative dose. One strategy is to start with a lower dose, 0.8 mg/kg, which was the average dose used in the retrospective study performed by Deal et al. This study supports starting with a more conservative initial dose since 84% of patients were at or above the anti-Xa goal.

Grady Health System is an inner city public hospital that serves a predominantly indigent patient population and includes a significant number of obese patients. Patients admitted to the hospital for anticoagulation treatment receive enoxaparin dosed 1 mg/kg twice daily using total body weight. Because of the significant obese patient population, clinical pharmacists often assist with dosing and monitoring in obese patients, including patients weighing more than 150 kg. Currently, there is no standard enoxaparin monitoring protocol and thus anti-Xa levels are ordered at the discretion of the physician or per the recommendation of a clinical pharmacist. Because of the ever increasing body habitus of the US patient population, there is a great need to determine optimal dosing regimens for obese patients in order to ensure therapeutic anti-Xa levels and prevent bleeding complications. Since previous studies have shown similar anti-Xa levels in patients with a BMI of 30-40 kg/m^2 and no increase in bleeding events, this study will investigate dosing in an underrepresented population of patients with a BMI >40 kg/m^2. Using the higher BMI cut-off will also allow for more patients with a weight above 150 kg which was also underrepresented in the trials.

The purpose of this study is to determine an effective enoxaparin dosing strategy in medically ill, morbidly obese patients to achieve therapeutic anti-Xa levels. If an optimal regimen is discovered the ultimate goal will be designing a dosing and monitoring protocol.

## 2. Design

### a. Sample

#### i. Inclusion

1. Treatment dosing of enoxaparin (twice daily)
2.  $BMI \geq 40 \text{ kg/m}^2$

#### ii. Exclusion

1.  $<18$  years of age
2. Renal dysfunction ( $\text{CrCl} < 30 \text{ ml/min}$ ) at any point during hospitalization while on enoxaparin
3. Pregnancy
4. Prisoners
5. Active bleeding
6. Already started on therapeutic enoxaparin and received  $>3$  consecutive doses
7. Therapeutic enoxaparin use within the last 3 months for  $>5$  consecutive days

### b. Setting

- i. The location of study and data collection will take place in Grady hospital

### c. Recruitment

- i. Inpatients initiated on enoxaparin treatment doses will be prospectively identified using a Pharmacy Report to query medication orders in the electronic medical record system.
- ii. Consent will occur in patient's hospital room once the medical team is notified of patient eligibility
- iii. Allowing 3 doses to be given prior to inclusion in the study will allow for equitable recruitment since clinical pharmacists may not be available during the evening hours to assist with initial dosing and recruitment

### d. Procedures

- i. Eligible patients will be approached while inpatient for written consent
- ii. Patients will be randomized in a 1:1 fashion into the 0.8mg/kg or 1 mg/kg group (using total body weight) stratified by BMI
  1. Doses will be rounded to the nearest 10mg due to graduations on syringe

#### iii. Initial anti-Xa levels

1. Order levels 4 hours after at least three consecutive study doses of enoxaparin (will allow levels drawn between 3-5 hrs). If the level is not drawn, it will be reordered after the next dose.
2. Therapeutic anti-Xa: 0.5-1.1 IU/ml (GHS therapeutic range)
3. Adjustments will be made according to the dosing nomogram until a therapeutic level is obtained (see appendix). If a bleeding event occurs an anti-Xa level will be obtained.

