##### 2. Post intervention

- a. Scr, CrCl

- b. Initial dose of enoxaparin (mg/kg and mg)
  - c. Initial anti-Xa level and timing of level
  - d. Number of hours post dose
    - i. Level at 4 hours
    - ii. Level within range of 3-5 hours
  - e. Total number of doses received prior to level
- 3. Subsequent doses of enoxaparin (mg/kg and mg)
- 4. Subsequent anti-Xa levels after dosing adjustments
- 5. Time to first therapeutic anti-Xa level
- 6. Total days on enoxaparin
- 7. Bleeding events
  - a. Decrease in Hgb
  - b. Site of bleed
  - c. Blood product use
  - d. INR at onset of bleeding event for patients on warfarin
  - e. Additional anticoagulants and antiplatelets (date initiated and dose)
  - f. Platelet count at onset of bleeding event
  - g. Anti-Xa level at onset of bleeding event
  - h. PT and/or aPTT if available
- v. Respondent Burden-Total respondent burden will be minimal and depend on the time it takes to consent. Laboratory work would have to be done for this medication regardless of whether they were in the study or not.

e. Study Objectives/Outcomes

- i. Primary Objective
  - 1. To determine if enoxaparin dosing using 0.8mg/kg is more effective for achieving therapeutic steady state anti-Xa levels in morbidly obese patients when compared to 1 mg/kg dosing. (Morbid obesity is defined as a BMI > 40 kg/m^2)
- ii. Secondary Objectives
  - 1. To compare time to therapeutic anti-Xa levels for both dosing regimens
  - 2. To compare anti-Xa levels for both dosing regimens
  - 3. To compare number of dose adjustments required to achieve therapeutic anti-Xa levels using a dosing nomogram
  - 4. To validate dosing nomogram used to adjust low molecular weight heparin doses
  - 5. To evaluate major and minor bleeding events
- iii. Primary Outcome
  - 1. Proportion of patients with an initial therapeutic anti-Xa level at steady state in each group
    - a. Peak anti-Xa drawn 3-5 hours post dose after receiving at least 3 consecutive doses
- iv. Secondary Outcomes
  - 1. Time to therapeutic anti-Xa level for both groups
  - 2. Mean/Median therapeutic anti-Xa level for both groups
  - 3. Mean/Median number of dose adjustments required to achieve therapeutic anti-Xa level for both groups
  - 4. Proportion of patients with major and minor bleeding events (will follow until anti-Xa level is therapeutic)

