- a. Major bleed: Hgb drop of  $\geq 2\text{g/dL}$ , transfusion of 2 or more units of blood products, or retroperitoneal, intraocular, or intracranial hemorrhage
- b. Minor bleed: bleeding events not meeting major bleed criteria
- f. Risks to participation
  - i. Patients started on enoxaparin will be at risk for bleeding complications which is a known risk for this medication. Risk will be reduced by obtaining anti-Xa levels and adjusting the dose as needed. Other possible risks may be , anemia, decrease in platelets, elevation of liver enzymes, diarrhea, and nausea
- g. Benefits to subject or future benefits
  - i. By completing this study a strategy for dosing enoxaparin may be established for obese patients that is safer and allows for quicker therapeutic levels.
- h. Data analysis
  - i. Sample Size- In order to detect a 15% difference in the primary endpoint with a 2-sided significance level of 0.05, 50 patients per dosing group is needed to provide 80% power.
  - ii. Statistical Analysis
    - 1. Descriptive statistics will be used for all variables. Primary outcome will be analyzed using chi-square. Time to event will be analyzed using survival curves and log rank test. Medians will be compared using wilcoxon rank test.

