#### Appendix A. Dosing Nomogram for Adjusting Enoxaparin

Anti-factor Xa level (IU/mL)	Hold Next Dose	Dose Change	Repeat Anti-factor Xa*
<0.35	No	Increase by 25%	4h after next dose
0.35-0.49	No	Increase by 10%	4h after next dose
0.5-1.1	No	No	---
1.2-1.5	No	Decrease by 20%	4h after next dose
1.6-2.0	No	Decrease by 30%	4h after next dose
>2.0	Until level is 0.5 IU/mL	Decrease by 40%	4h after next dose

Adapted from CHEST 2001 and adjusted per institutional procedures

\*Will obtain level if CrCl<30 ml/min or bleeding event

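### The initial anti-Xa level is reordered only if it was not drawn, so the plan provides no redraw on the assigned dose when the level falls outside the 3-5 hour window that the primary outcome requires

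*Combined protocol and SAP*

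**What the plan says.** All of these places are in the combined protocol and SAP.

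- **Procedures, Initial anti-Xa levels (2.d.iii), item 1.** The level is ordered for 4 hours after at least three consecutive study doses, with a tolerance: "will allow levels drawn between 3-5 hrs". The recovery rule follows: "If the level is not drawn, it will be reordered after the next dose". No other reason for reordering is given.
- **Same section, item 3.** "Adjustments will be made according to the dosing nomogram until a therapeutic level is obtained". Nothing is said about when the sample must have been taken for the nomogram to apply.
- **Data Collection (2.d.iv), Post intervention.** The form captures hours since the dose and "Level within range of 3-5 hours".
- **Primary Outcome (2.e.iii).** The outcome is the proportion of patients whose initial steady-state level is therapeutic, specified as "Peak anti-Xa drawn 3-5 hours post dose after receiving at least 3 consecutive doses".
- **Data analysis (2.h).** The primary outcome is tested by chi-square. The section names no analysis set and no rule for a missing or mistimed level. The sample size is 50 per group.
- **Appendix A.** The nomogram acts on the measured value alone. The 0.5-1.1 row has no dose change and no repeat. Every other row changes the dose and repeats the level "4h after next dose"; the row above 2.0 also holds the next dose.

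**The concern.** Timing is part of the endpoint definition, yet the rule that protects the endpoint responds only to a missing sample. A mistimed sample is a third possibility: it was drawn, but it does not meet the definition. The plan sets a tolerance and records compliance with it, so it allows for the window being missed, but it says nothing about what happens then.

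At stake is the sole primary outcome. Once the nomogram has changed a patient's dose, no later sample can show what the randomised starting dose achieved. A patient with no usable level must then be dropped, scored by a convention that has not been stated, or scored on a level that the definition excludes. Whether the dose is changed depends on the measured value, so the losses could also differ between arms.

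**Working it through.** **Step 1. Follow the text literally for each possible draw.**

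- *No sample taken.* Item 1 reorders after the next dose. The patient is still on the assigned dose, so the endpoint is protected.
- *Sample within 3-5 hours.* It meets the Primary Outcome definition, so the endpoint is obtained.
- *Sample outside 3-5 hours, reading 0.5-1.1.* A sample was drawn, so item 1 is not triggered. Appendix A gives no dose change and no repeat. The patient stays on the assigned dose and an in-window level could still be obtained, but none is planned.
- *Sample outside 3-5 hours, reading out of range.* Item 1 is not triggered. Appendix A changes the dose and then repeats. The repeat measures the adjusted dose, so a valid initial level on the randomised dose is lost. For example, a reading of 1.2-1.5 on 1 mg/kg brings a 20% decrease: 1.0 × (1 − 0.20) = 0.8 mg/kg, which is the other arm's starting dose (before rounding to the nearest 10 mg).

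**Step 2. Check the plan's own sample size.** The plan reads "In order to detect a 15% difference in the primary endpoint with a 2-sided significance level of 0.05" and gives 50 per group for 80% power. No reference rate is stated. The Background reports 45% therapeutic on 1 mg/kg in a cohort with BMI above 30. It is used here only as an illustration, with 45% + 15 points = 60% in the other arm and a mean rate of 0.525.

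n per group = [1.960 × √(2 × 0.525 × 0.475) + 0.842 × √(0.45 × 0.55 + 0.60 × 0.40)]² / 0.15²
= (1.384 + 0.588)² / 0.0225 ≈ 173.

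The figure of 50 is therefore not reproduced at this rate. Power with 50 per group is 32.2%. That shortfall is a separate matter and neither supports nor weakens this point. It matters here only because there is no slack to absorb further loss.

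**Step 3. Size of the loss.** The documents give no frequency of mistimed draws, so *f* is an assumption, and the figures also assume that no mistimed level is redrawn. Evaluable per group = 50 × (1 − f). Number to randomise to keep 50 evaluable = 50 / (1 − f), rounded up. Power is for 45% vs 60%.

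| f | Evaluable per group | Randomise per group to keep 50 | Power |
|---|---|---|---|
| 0 | 50 | 50 | 32.2% |
| 5% | 47.5 | 53 | 30.8% |
| 10% | 45 | 56 | 29.4% |
| 20% | 40 | 63 | 26.6% |
| 30% | 35 | 72 | 23.8% |

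**Step 4. Why the counting rule matters.** Suppose f = 20% in both arms, unrelated to the result. If these patients are excluded, the rates stay at 45% and 60% on 40 per group. If they are counted as not therapeutic, the rates become 0.8 × 45 = 36% and 0.8 × 60 = 48%, and the difference shrinks from 15 to 12 points. The plan does not say which applies.

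**The case against.** The best defence is that the reorder sentence directly follows the 4-hour order and its 3-5 hour tolerance. The level that was not drawn may mean the windowed level, so that a sample at 7 hours counts as not drawn. That reading is available, and the documents do not exclude it. But it is not stated, and staff applying the rule on the ward may well take it literally. Recording draw times is also ordinary compliance capture and says nothing about how often draws are mistimed.

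A reader might infer three stronger things, which the documents do not support:

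- *Every mistimed draw costs the patient a valid endpoint for good.* This is true only where the dose is changed. After a mistimed reading of 0.5-1.1 the patient is still on the assigned dose.
- *Mistimed levels are never repeated.* Out-of-range ones are repeated, but after the dose change.
- *Late samples would be scored and would bias the comparison.* Scoring them would depart from the Primary Outcome definition. The size of any bias also rests on assumptions: a half-life of 4.5-7 hours, lognormal peaks with log-SD 0.3-0.5, and the mean of 1.17 IU/mL from the Background, which comes from a BMI above 30 cohort. Under these, 48-87% of 1 mg/kg patients with a true peak above 1.1 would read in range at 7 hours, but only 25-55% at 5.5 hours. Against this, 9-47% of truly therapeutic patients would read below 0.5 at 7 hours. The net rise in the scored therapeutic rate is 7.7 to 33.1 points in that arm. The half-life and spread are not in the documents, and neither is the effect on the difference between arms.

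**Conclusion.** The concern holds in a limited form. Taken literally, the plan schedules no in-window level on the randomised dose for a patient whose initial level was drawn outside 3-5 hours. Where the nomogram then changes the dose, that level cannot be recovered; where it does not, the level could still be obtained but nothing in the plan obtains it. The plan also does not say how such a patient enters the chi-square test.

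The documents do not fix the size. Assuming 5-30% of initial draws are mistimed and not redrawn, about 47 to 35 of 50 per group stay evaluable, with no allowance stated. No direction of bias is claimed. The change is worth making because it concerns a stated rule that guards the only primary outcome and costs little, whatever the true frequency.

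**What to change.** 1. In Initial anti-Xa levels, item 1, extend the trigger so that the level is reordered if it was not drawn, or was drawn outside 3-5 hours after the dose.
2. In Primary Outcome, state that only an in-window level on the randomised dose counts.
3. In Data analysis, define the analysis set and say how patients without such a level are counted (excluded, or counted as not therapeutic), with the other choice as a sensitivity analysis. Report their number by arm, with any dose change made on an out-of-window level.
4. The sponsor must reconcile Initial anti-Xa levels, Primary Outcome and Appendix A on whether the nomogram, including its hold row, applies to a level drawn outside the window. The extended trigger is a measurement rule and should not be read as overriding any nomogram row. No dosing rule is proposed here.

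The cost is a few sentences of protocol text and, in mistimed patients only, one extra draw through the existing reorder process. Their initial level would come about one dosing interval later (roughly 12 hours on twice-daily dosing).

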#### iv. Data Collection

##### 1. Baseline Data

- a. TBW, height, BMI
- b.  $BMI = TBW(\text{kg})/\text{height} (\text{m})^2$
- c. Age, Sex, Race
- d. Scr, CrCl (Cockcroft-Gault equation)
- e. Indication for treatment

##### 2. Post intervention

- a. Scr, CrCl

- b. Initial dose of enoxaparin (mg/kg and mg)
  - c. Initial anti-Xa level and timing of level
  - d. Number of hours post dose
    - i. Level at 4 hours
    - ii. Level within range of 3-5 hours
  - e. Total number of doses received prior to level
- 3. Subsequent doses of enoxaparin (mg/kg and mg)
- 4. Subsequent anti-Xa levels after dosing adjustments
- 5. Time to first therapeutic anti-Xa level
- 6. Total days on enoxaparin
- 7. Bleeding events
  - a. Decrease in Hgb
  - b. Site of bleed
  - c. Blood product use
  - d. INR at onset of bleeding event for patients on warfarin
  - e. Additional anticoagulants and antiplatelets (date initiated and dose)
  - f. Platelet count at onset of bleeding event
  - g. Anti-Xa level at onset of bleeding event
  - h. PT and/or aPTT if available
- v. Respondent Burden-Total respondent burden will be minimal and depend on the time it takes to consent. Laboratory work would have to be done for this medication regardless of whether they were in the study or not.

e. Study Objectives/Outcomes

- i. Primary Objective
  - 1. To determine if enoxaparin dosing using 0.8mg/kg is more effective for achieving therapeutic steady state anti-Xa levels in morbidly obese patients when compared to 1 mg/kg dosing. (Morbid obesity is defined as a BMI > 40 kg/m^2)
- ii. Secondary Objectives
  - 1. To compare time to therapeutic anti-Xa levels for both dosing regimens
  - 2. To compare anti-Xa levels for both dosing regimens
  - 3. To compare number of dose adjustments required to achieve therapeutic anti-Xa levels using a dosing nomogram
  - 4. To validate dosing nomogram used to adjust low molecular weight heparin doses
  - 5. To evaluate major and minor bleeding events
- iii. Primary Outcome
  - 1. Proportion of patients with an initial therapeutic anti-Xa level at steady state in each group
    - a. Peak anti-Xa drawn 3-5 hours post dose after receiving at least 3 consecutive doses
- iv. Secondary Outcomes
  - 1. Time to therapeutic anti-Xa level for both groups
  - 2. Mean/Median therapeutic anti-Xa level for both groups
  - 3. Mean/Median number of dose adjustments required to achieve therapeutic anti-Xa level for both groups
  - 4. Proportion of patients with major and minor bleeding events (will follow until anti-Xa level is therapeutic)

- a. Major bleed: Hgb drop of  $\geq 2\text{g/dL}$ , transfusion of 2 or more units of blood products, or retroperitoneal, intraocular, or intracranial hemorrhage
- b. Minor bleed: bleeding events not meeting major bleed criteria
- f. Risks to participation
  - i. Patients started on enoxaparin will be at risk for bleeding complications which is a known risk for this medication. Risk will be reduced by obtaining anti-Xa levels and adjusting the dose as needed. Other possible risks may be , anemia, decrease in platelets, elevation of liver enzymes, diarrhea, and nausea
- g. Benefits to subject or future benefits
  - i. By completing this study a strategy for dosing enoxaparin may be established for obese patients that is safer and allows for quicker therapeutic levels.
- h. Data analysis
  - i. Sample Size- In order to detect a 15% difference in the primary endpoint with a 2-sided significance level of 0.05, 50 patients per dosing group is needed to provide 80% power.
  - ii. Statistical Analysis
    - 1. Descriptive statistics will be used for all variables. Primary outcome will be analyzed using chi-square. Time to event will be analyzed using survival curves and log rank test. Medians will be compared using wilcoxon rank test.

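### Secondary outcome 2 averages only 'therapeutic' anti-Xa levels, so no listed outcome compares the full initial level between the two doses

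*Combined protocol and SAP*

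**What the plan says.** Section 2.e.ii, item 2, sets an unrestricted objective: "To compare anti-Xa levels for both dosing regimens". The matching entry in section 2.e.iv, item 2, adds a qualifier: "Mean/Median therapeutic anti-Xa level for both groups". The other three secondary outcomes are a time, a count of dose adjustments and a bleeding proportion, so this is the only one whose value is an anti-Xa level.

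Section 2.d.iii, item 2, defines therapeutic as 0.5–1.1 IU/ml. Item 3 makes that range the stopping point for titration: "Adjustments will be made according to the dosing nomogram until a therapeutic level is obtained".

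The primary outcome uses the initial level only as in range or not: "Proportion of patients with an initial therapeutic anti-Xa level at steady state in each group". The level itself is a data item in section 2.d.iv ("Initial anti-Xa level and timing of level"). Section 2.h.ii plans descriptive statistics for all variables and a Wilcoxon test for medians, without naming the variables to be tested.

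**The concern.** The objective leaves out the word therapeutic and the outcome puts it in. An analyst who follows the protocol's own definition would compare only values between 0.5 and 1.1 IU/ml in both arms. That permits two analyses:

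- **Reading (a): initial levels that are in range.** Patients enter according to whether they met the primary endpoint, which is determined after randomisation and expected to differ by arm. The arms are no longer compared as randomised.
- **Reading (b): the first in-range level, at whatever dose produced it.** Out-of-range patients have been titrated into the same band, so the value no longer reflects only the assigned dose.

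The dichotomised primary outcome does not fill the gap. It cannot show whether out-of-range levels are high or low, or by how much exposure differs. Over-exposure with weight-based dosing is the worry raised in the Background.

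**Working it through.** **1. How the document uses the word.** In the primary outcome, therapeutic is a state the initial level is or is not in. Secondary outcome 1 is the time to reach that state. Outcome 3 is "Mean/Median number of dose adjustments required to achieve therapeutic anti-Xa level for both groups", and the bleeding outcome says patients "will follow until anti-Xa level is therapeutic". All four use the in-range sense. Nothing says that outcome 2 uses a different one.

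**2. Inputs for sizing the effect.** The plan states no figure for this outcome, so there is none to reproduce.

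- From the documents: arms of 0.8 and 1 mg/kg, 50 patients per arm, two-sided 0.05, range 0.5–1.1 IU/ml, the Appendix A nomogram, and a mean of 1.17 IU/ml at 1 mg/kg twice daily in a cited BMI >30 study (Background).
- Assumed: levels proportional to dose, so the 0.8 mg/kg mean is 0.8 × 1.17 = 0.936; the same CV in both arms, 20–60% (the documents give no SD); normal or log-normal levels; a level in all 50 patients per arm. Because 1.17 comes from a less obese population, a mean of 1.0 (0.80 at the lower dose) is also shown.
- For reading (b): Appendix A is applied until the level is in range, values in its 1.1–1.2 and 1.5–1.6 gaps go to adjacent rows, and repeat levels carry no within-patient noise.

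**3. Reading (a) by hand, normal, CV 30%.** With limits z₁ = (0.5 − μ)/σ and z₂ = (1.1 − μ)/σ, the fraction kept is Φ(z₂) − Φ(z₁). The median of those kept is μ + σ·Φ⁻¹[(Φ(z₁) + Φ(z₂))/2].

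- 1 mg/kg: μ = 1.17, σ = 0.351. Kept: 0.421 − 0.028 = 0.393. Median: 1.17 + 0.351 × (−0.757) = 0.904.
- 0.8 mg/kg: μ = 0.936, σ = 0.281. Kept: 0.720 − 0.060 = 0.660. Median: 0.936 + 0.281 × (−0.278) = 0.858.
- Difference: 0.904 − 0.858 = 0.046, against a true 1.17 − 0.936 = 0.234. About 20% is left (0.046/0.234), from 39% of one arm and 66% of the other.

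**4. Both readings by simulation.** Median differences are in IU/ml. Power is for the Wilcoxon test, starting from 50 per arm.

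| Mean at 1 mg/kg | Distribution | CV | All initial levels | (a) | (b) | Power: all / (a) / (b) |
|---|---|---|---|---|---|---|
| 1.17 | normal | 20% | 0.234 | 0.073 | 0.050 | 1.00 / 0.38 / 0.76 |
| 1.17 | normal | 40% | 0.234 | 0.030 | 0.039 | 0.76 / 0.07 / 0.34 |
| 1.17 | normal | 60% | 0.235 | 0.014 | 0.032 | 0.43 / 0.05 / 0.19 |
| 1.17 | log-normal | 20% | 0.230 | 0.099 | 0.062 | 1.00 / 0.74 / 0.92 |
| 1.17 | log-normal | 40% | 0.217 | 0.066 | 0.062 | 0.79 / 0.19 / 0.60 |
| 1.17 | log-normal | 60% | 0.201 | 0.038 | 0.103 | 0.49 / 0.08 / 0.37 |
| 1.0 | normal | 20% | 0.200 | 0.122 | 0.134 | 1.00 / 0.91 / 0.99 |
| 1.0 | normal | 40% | 0.200 | 0.048 | 0.112 | 0.76 / 0.12 / 0.52 |
| 1.0 | normal | 60% | 0.200 | 0.023 | 0.102 | 0.42 / 0.06 / 0.26 |
| 1.0 | log-normal | 20% | 0.196 | 0.135 | 0.144 | 1.00 / 0.97 / 1.00 |
| 1.0 | log-normal | 40% | 0.186 | 0.068 | 0.152 | 0.80 / 0.24 / 0.71 |
| 1.0 | log-normal | 60% | 0.171 | 0.037 | 0.171 | 0.50 / 0.09 / 0.41 |

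At mean 1.17, reading (a) leaves 6% (0.014/0.235) to 43% (0.099/0.230) of the median difference. It keeps 29–49% of the 1 mg/kg arm against 40–82% of the other. Reading (b) leaves 14% to 51%.

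At mean 1.0, reading (a) leaves half or more only at CV 20% (normal) or up to 30% (log-normal). Reading (b) leaves 51–100% of the median difference, although the mean difference still falls from 0.20 to 0.05–0.13.

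**5. Fit to the cited study.** If its goal range was also 0.5–1.1 (not stated), 45% in range with mean 1.17 implies a log-normal CV of about 25%. The median difference of 0.227 then falls to 0.092 under (a) and 0.060 under (b), and power from 0.99 to 0.54 and 0.84.

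**The case against.** The strongest reply is that therapeutic here is loose wording for the level on treatment dosing. Outcome 2 pairs with objective 2, the data are collected, and the Wilcoxon sentence does not exclude the initial level. That may be what was intended. But the document defines the term and uses it consistently everywhere else, and no sentence ties a between-arm test to the unrestricted level. If loose wording was meant, the same edit is needed.

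Second, the loss is not uniform. At mean 1.0, reading (b) can come close to the full comparison (log-normal, CV 30%: power 0.91 against 0.96). This stands as a limit on the size of the problem. How much survives depends on where levels happen to fall relative to the band, which the trial cannot know in advance. The upper end is also generous: adding an assumed 15% log-scale noise to repeat levels lowers the mean-1.0 medians under (b) from 0.10–0.17 to about 0.07–0.13.

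Third, the Background reports a closer population (BMI ≥40, median dose 0.8 mg/kg) with group means of 0.81 and 1.12 IU/ml. Scaled to 1 mg/kg these are 0.81/0.8 = 1.01 and 1.12/0.8 = 1.40. So the milder mean-1.0 case is plausible, but so is a worse one. At mean 1.40, normal, CV 30%, the formula in step 3 gives in-range medians of 0.921 and 0.898, a difference of 0.023 against a true 0.28.

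Finally, objective 2 does not itself say initial level. That is correct, but the initial level is the only one measured at the randomised dose in every patient who has a level.

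**Conclusion.** The concern holds. Followed as written, secondary outcome 2 compares either a subset selected on the primary endpoint or levels already titrated into a common band, and neither measures the exposure difference that objective 2 asks about.

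Under reading (a), less than half of the median difference remains in every mean-1.17 case and in most mean-1.0 cases. Under reading (b) the attenuation ranges from severe to none for the median. The sizes rest on assumed dose proportionality, equal CVs and assumed means. The selection problem in (a) and the titration problem in (b) do not depend on those numbers. The matter is confined to one secondary outcome; the primary analysis and the sample size are untouched.

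**What to change.** Reword secondary outcome 2 as the initial steady-state peak anti-Xa level, drawn 3–5 hours post dose after at least three consecutive study doses and before any adjustment, in all randomised patients with such a level, whether in or out of range. Name it in section 2.h.ii as compared by Wilcoxon rank-sum, with a median difference and 95% confidence interval. If an in-range or final level is also wanted, report it descriptively by arm and say which of the two it is.

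The cost is a wording change. The initial level and its timing are already collected and the Wilcoxon test is already planned. No additional data, patients or change to treatment are involved.
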